#### **Capacity to Provide Consent:**

**Do you anticipate using surrogate consent or is research being done in a population where capacity to consent may be questionable?**

No

---

#### **Research Aims & Abstracts**

---

#### **Research Question(s)/Hypothesis(es):**

Aim 1: Does Longer, milder SR, as observed in individuals with SSD lead to positive energy balance? Hypothesis 1a: SR will lead to increased total adipose tissue mass, as assessed using MRI, relative to HS. We will perform repeated measure linear mixed model analyses separately for adipose tissue mass increase and weight gain (as the response). Hypothesis 1b: EE, assessed by doubly labeled water, and physical activity level, monitored daily by actigraphy, will be lower during SR relative to HS. Aim 2: Is the increased EI observed in acute SR studies maintained over time? Hypothesis 2a: EI, assessed by 3-d food records, will be greater during a period of SR relative to HS. This will be mostly due to increased fat and carbohydrate intakes. Hypothesis 2b: Neural responses to food stimuli, assessed by fMRI after 6 wk of SR or HS, will indicate increased

activity in networks associated with reward and food valuation (insula, orbitofrontal cortex) during a period of SR relative to HS. These responses will be correlated with intakes of high carbohydrate and high fat foods (hypothesis 1a) and ghrelin. Connectivity of the networks involved in reward valuation at rest will be stronger after SR compared to HS and synchrony of the DMN will be reduced after SR compared to HS. **Aim 3:** Does Longer, milder SR, as observed in individuals with SSD adverse cardiometabolic risk profile? **Hypothesis 3a:** SR will lead to increased glucose, insulin, triglycerides, and reduced high density lipoprotein cholesterol and adiponectin relative to HS. **Hypothesis 3b:** Increased adiposity and poor diet quality (higher fat and carbohydrates) after SR will partially explain the adverse cardio-metabolic risk profile associated with SR. **Aim 4.** To determine whether long-term mild SR, relative to HS, challenges acute cognitive outcomes in older and younger adults. **Hypothesis 4a.** Mild SR will induce cognitive decline, assessed with the NIH Toolbox, which will be greater in older relative to younger adults. **Aim 5.** To determine whether the effects of SR on cognitive outcomes are moderated by brain atrophy and small vessel cerebrovascular disease in younger and older adults. **Hypothesis 5a.** The effect of mild SR on cognition will be greater among individuals with greater amounts of cortical thinning, smaller hippocampi, and greater WMH volume. This effect will be larger in older relative to younger adults. **Aim 6.** To determine whether changes in metabolic or hormonal profiles mediate changes in cognitive function as a result of SR. **Hypothesis 6a.** The effect of mild SR on cognition will be mediated by changes in hormones (leptin, adiponectin, and insulin).

---

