
between sleep duration and body weight regulation". This will be fulfilled should the proposed study be funded. Clinical intervention studies, on the other hand, have consistently shown that SR increases EI in normal sleepers [16-19] above and beyond the added cost of waking EE [20]. Criticisms of these studies are that they have employed short intervention periods, ranging from a single night to 14 d, and have tested very restrictive sleep schedules, typically 3 h less than Habitual Sleep (HS) (4-5.5 h TIB). Although these studies provide information on causality, many questions remain unanswered: Does longer, milder SR as observed in individuals with SSD, lead to positive energy balance (Aims 1 & 2)? Is the increased EI observed in acute studies maintained over time and if so, does it result in increased adiposity (Aim 1) and adverse cardiometabolic risk profile (Aim 3)? The proposed study will answer these critical questions.

In addition to being a risk factor for cardiovascular disease, type 2 diabetes, and obesity [21], short sleep duration (SSD) is related to an increased risk of cognitive impairment in older adults [22,23]. Individuals at lowest risk of cognitive impairment are those with adequate sleep duration of 7-8 h/night [22]. SSD may induce cognitive impairment in older adults by promoting Alzheimer's disease pathology directly. Indeed recent studies showed that inadequate sleep is associated with Alzheimer's disease biological markers, including cerebrospinal fluid measures of beta amyloid and measures of fibrillar amyloid derived from positron emission tomography (**PET**) [24]. Intervention studies demonstrated increased circulating plasma levels of amyloid beta in young adults [25] and increased fibrillar brain amyloid beta in older adults [26] following one night of sleep deprivation. However, there are no studies to date that have evaluated the impact of long-term, sustained short sleep duration, mimicking the widespread sleep behavior of U.S adults, on cognitive function in older adults, and the mediators and moderators of the effect of sleep deprivation on cognitive outcomes are poorly understood. The proposed supplementary study examines the effect of sleep restriction on cognitive outcomes in older adults and tests the possibility that cerebral atrophy, cerebrovascular disease, and hormonal markers mediate this effect.

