Sample size determination. We will enroll 66 participants and expect 50 to complete the study. This drop-out rate accounts for participant non-compliance. In our previous Sleep Study, our completion rate was 90%. We expect a larger drop-out rate in the proposed study due to the longer duration of each treatment phase, and we also anticipate dismissing some participants due to non-compliance. Each participant will undergo 2 study phases, and each response variable will be measured at least once per phase. Thus, for each response measure we will have at least  $50 \times 2$  paired observations. We have analyzed preliminary data consisting of a number of measurements from 2 overweight women from our Pilot Study. Based on preliminary data analysis we have estimated an effect size (mean paired difference) of  $0.69 \pm 0.36$  g for fat mass and an effect size (mean paired difference) of  $0.91 \pm 0.65$  g for weight gain. This translates to very large effect sizes of 1.92 (fat mass) and 1.4 (weight gain) for paired t-tests. With these effect sizes we have more than 99% power for paired t-tests.] We have estimated the EI effect size to be  $295.9 \pm 116.3$  kcal [8]. The effect size for a paired t-test (effect size divided by the standard deviation) for a paired t-test is >2, which is a very large effect size for paired t-test. This means with  $50 \times 2$  paired samples, we have >80% power for paired t-test. In [name] et al. 2011 [8], we also reported an effect size of  $20.7 \pm 6.8$  g for fat intake and an effect size of  $57.9 \pm 32.6$  g for carbohydrate intake. This translates to very large effect sizes of 3.04 and 1.78, respectively for fat and carbohydrates for paired t-test. With these effect sizes we have >80% power for paired t-test. Moreover, using the R^2 value from our linear model analysis of [name] et al. 2011, we determined that we have >80% power for proposed linear mixed model analyses (as described in statistical plan) with energy balance, fat and carbohydrate intakes. Thus, we have very good power overall, which will be useful in our primary analyses as well as in exploring sex differences. Statistical plan. Exploratory data analyses for physiological, anatomical, biomarker and intakerelated responses will be performed using R, SAS and other software. As part of the analysis, we will compute descriptive statistics for each variable. In particular, we will compute the proportion, mean, variance, standard error and the range of continuous variables and frequency and mode for discrete variables. Descriptive statistics will be computed for each specific sleep phase. In addition, correlation coefficients between the variables will be computed and scatter plots will be checked for linear relationships. The correlations and scatter plots help assess the degree of collinearity among variables, which will be useful for interpreting regression-based linear mixed model analyses discussed later. The data will be tested for normality, and if needed an appropriate transformation will be used on the raw data to make the normal approximation better. We will have a comprehensive strategy to deal with missing data. We will study missingness to decide if the data are missing at random or missing completely at random. Missing rates will also be estimated for each variable. Missing values will be imputed, as appropriate. We will fit a linear mixed model to analyze the data. Treatments (sleep duration: SR vs. HS) will be fixed effects and subjects a random effect. As we are collecting data from two phases for each subject, we will test for carryover effects by using a treatment x phase interaction in an initial version of each linear model. If the interaction term is not significant then we will rebuild the linear model without the interaction term. The other independent variables (covariates) will be sex, age, baseline BMI, and race/ethnicity. If required anywhere in the analysis plan, p-values will be adjusted for multiple comparisons. Sp. Aim 1: Hypothesis 1a. SR will lead to increased total adipose tissue mass, as assessed using MRI, relative to HS. We will perform repeated measure linear mixed model analyses separately for adipose tissue mass increase and weight gain (as the response). Sleep duration (SR vs. HS) and the covariates will be used as independent variables. Subject will be used as a random effect. Paired t-test and Wilcoxon test will be used to determine whether the SR and HS have different

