
effects on weight gain and adipose tissue mass increase. Hypothesis 1b. EE, assessed by DLW, and physical activity level, monitored daily by actigraphy, will be lower during SR relative to HS. We will perform repeated measure linear mixed model analyses separately for DLW and actigraphy-derived variables as the responses. Sleep duration (SR vs. HS) and the covariates will be used as independent variables. Subject will be used as a random effect. Paired t-test and Wilcoxon test will be used to determine whether SR and HS have different effects on DLW and actigraphy measures. Sp. Aim 2: Hypothesis 2a. EI, assessed by [3-d food records], will be greater during a period of SR relative to HS. This will be mostly due to increased fat and carbohydrate intakes. We will perform a repeated measure linear mixed model analyses separately with each EI measure (as the response) and sleep duration (SR vs. HS) and the covariates as independent variables. Subject will be used as a random effect. Paired t-test and Wilcoxon test will be used to determine whether the SR and HS have different effects on EI measures. Hypothesis 2b. Neural responses to food stimuli, assessed by fMRI after 6 wk of SR or HS, will indicate increased activity in networks associated with reward and food valuation (insula, orbitofrontal cortex) during a period of SR relative to HS. These responses will be correlated with intakes of high carbohydrate and high fat foods (hypothesis 1a) and [ghrelin]. Connectivity of the networks involved in reward valuation at rest will be stronger after SR compared to HS and synchrony of the DMN will be reduced after SR compared to HS. Sp. Aim 3: Hypothesis 3a. SR will lead to [increased glucose, insulin, triglycerides, and reduced highdensity lipoprotein cholesterol and adiponectin relative to HS.] We will perform repeated measure linear mixed model analyses separately for each of glucose, insulin, triglycerides, high-density lipoprotein cholesterol and adiponectin. Sleep duration (SR vs. HS) and the covariates will be used as independent variables. Subject will be used as a random effect. One-sided paired t-test and Wilcoxon test will also be used to determine whether the SR and HS have different effects on the cardio-metabolic risk profiles, as well as the direction of the effects. Hypothesis 3b. Increased adiposity and poor diet quality (higher fat and carbohydrates) after SR will partially explain the adverse cardio-metabolic risk profile associated with SR. We will select the cardiometabolic risk profile variables that are adversely associated with SR. Then, we will compute the difference in those variables in SR vs. HS (i.e. the value of each variable in SR minus the value of that variable in HS). Using a linear model analysis, we will test if these differences are associated with increased adiposity and poor diet quality. If, for some variables, there are multiple observed differences for each subject then a linear mixed model analysis will be used with subject as a grouping variable. A separate analysis will be performed for each such difference, with the difference as the response variables and adiposity, food quality variables and the covariates as dependent variables. *Linear Mixed Model Analyses.* We will fit a linear mixed model to analyze the data. Treatments (SR vs. HS) will be used as fixed effects and subject will be used a random effect. The other independent variables, such as demographic variables, will be covariates. Those covariates will be removed if they do not significantly contribute to the model. Aim 4: (To determine whether long-term mild SR, relative to HS, challenged acute cognitive outcomes in older and younger adults. Hypothesis 4a. Mild SR will induce cognitive decline, assessed using with the NIH Toolbox, which will be greater in older relative to younger adults.) Outcomes are measures from the NIH Toolbox. Each outcome will be analyzed in separate linear mixed model analyses, for older and young participants, as detailed in "*Linear Mixed Model Analyses*" section above. Sleep (SR vs. HS), along with phase (1 vs. 2), carryover effects, and covariates (if they are found to be significant in an initial analysis) will be used in the model. Subject will be used as a random effect. Then, we will pool the datasets to include both older and young participants. In the pooled dataset, we will use the average differences in NIH Toolbox measures (from HS to SR) as outcomes in linear model analysis. Age group (older vs. younger) will be used as main predictor variable. We will also apply covariates as independent variables, if they are found to be significant in an initial analysis. We will use unpaired t-test on the average difference in

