#### Appetite & food intake measurements.

Throughout the study, participants will self-select their food intake in a freeliving situation. Food intake will be assessed at baseline, wk 3, and wk 6 by 3-d food records (2 weekdays and one weekend day) using a free electronic app, such as MyFoodCircle, HealthWatch 360, or other similar app; or on paper. Participants could be asked to provide pictures of their food to assist in data collection. In the proposed study, we are interested in qualitative assessment of diet and comparison of intakes between phases. Nonetheless, quantitative assessments will also be available. Since participants will be blind to the true objective of our study, we do not expect reporting error to systematically vary based on study phase and can have confidence in our measurement tool. The within-subject study design is essential in this regard. Moreover, the true assessment of energy balance is change in body composition: weight gain invariably signifies positive energy balance whereas weight loss represents negative energy balance. Energy and macronutrient intakes will be assessed using the University of Minnesota Nutrition Data System for Research (NDSR, Minneapolis, MN).

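### Aim 2 asks whether the intake increase is maintained, but the Hypothesis 2a analysis contains nothing that separates week 3 from week 6

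*Combined protocol and SAP*

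**What the plan says.** The question about time appears twice. In the Research Question(s)/Hypothesis(es) section, Aim 2 is "Is the increased EI observed in acute SR studies maintained over time". The Study Purpose and Rationale section asks "Is the increased EI observed in acute studies maintained over time and if so, does it result in increased adiposity (Aim 1"), and criticises earlier intervention studies for short exposure, "ranging from a single night to 14 d".

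The data have a time structure. Under Appetite & food intake measurements: "Food intake will be assessed at baseline, wk 3, and wk 6 by 3-d food records".

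The hypothesis is narrower than the aim. Hypothesis 2a states that "EI, assessed by 3-d food records, will be greater during a period of SR relative to HS". Its analysis in Statistical Procedures is "We will perform a repeated measure linear mixed model analyses separately with each EI measure (as the response) and sleep duration (SR vs. HS"), plus the covariates and a random subject effect, with a paired t-test and a Wilcoxon test in support. The general model says "The other independent variables (covariates) will be sex, age, baseline BMI, and race/ethnicity". The only interaction it names concerns the crossover period: "we will test for carryover effects by using a treatment x phase interaction in an initial version of each linear model", removed if not significant.

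For intake, the plan names no week effect, sleep-by-week interaction or week-6 contrast. It does not say which of the three records per phase enter the response, or which value the paired tests use.

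**The concern.** A model whose only sleep term is SR vs HS returns one difference per intake measure. An effect of 300 kcal at week 3 and none at week 6 gives the same pooled estimate as a steady 150 kcal. Week 6 is the longest exposure the trial offers, and the rationale makes the adiposity question depend on the intake effect lasting. If the pooled result is positive, the plan supplies no estimate that would show a reader whether the effect was still there at the end of the phase.

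**Working it through.** **Inputs from the plan.** The intake effect is 295.9 ± 116.3 kcal, used in Statistical Procedures as the mean and SD of a paired difference. Expected completers are 50 (same section). The Subjects section reports 36 completers.

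**Assumed.** Two-sided alpha 0.05. True SR–HS difference 300 kcal at week 3 (the plan's figure, rounded) and 0 at week 6. SD of the SR–HS difference at one visit, *s*, 500 kcal (range 400–650). Correlation *r* between visits' differences 0.3–0.5. The plan gives none of these apart from the source of the 300.

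**Step 1: the plan's own figure.** d = 295.9/116.3 = 2.54. A paired t-test with n = 50 has power above 99.9%, which agrees with the stated figure of more than 80%. That power is for SR vs HS and does not address change between weeks.

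**Step 2: what the pooled model estimates.** With complete records it is the mean of the visit-specific differences:
- weeks 3 and 6 only: (300 + 0)/2 = 150 kcal
- baseline also in the response, with no true difference there: (0 + 300 + 0)/3 = 100 kcal

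**Step 3: SD of that mean.** For two records it is s·√((1+r)/2), which at s = 500 is 403 (r = 0.3) or 433 (r = 0.5). For three records it is s·√((1+2r)/3), which is 365 or 408.

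**Step 4: probability of a significant pooled result** (noncentral t, n − 1 df, noncentrality d·√n, s = 500):

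| Records pooled | r | d | n = 36 | n = 50 |
|---|---|---|---|---|
| wk 3, wk 6 | 0.3 | 150/403 = 0.372 | 58% | 73% |
| wk 3, wk 6 | 0.5 | 150/433 = 0.346 | 52% | 67% |
| baseline, wk 3, wk 6 | 0.3 | 100/365 = 0.274 | 36% | 48% |
| baseline, wk 3, wk 6 | 0.5 | 100/408 = 0.245 | 30% | 40% |

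Over s = 400–650 the two-record figures run from 34% to 77% (n = 36) and from 46% to 90% (n = 50). If the plan's 116.3 is taken as the visit-level SD, the pooled test is significant in more than 99.9% of trials at either n.

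**Step 5: the week-6 contrast.** In the fade case it is significant only at the nominal 5%, about 2.5% in the direction SR > HS. If a 300 kcal effect is maintained, d = 300/500 = 0.6 and power is 94% (n = 36) or 99% (n = 50). At s = 650 it is 77% or 89%. Its standard error exceeds that of the two-record mean by a factor of 500/433 = 1.15 to 500/403 = 1.24.

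**The case against.** The strongest reply is that the plan makes Aim 2 operational through Hypothesis 2a, a phase-level contrast that the stated model does test. Weeks 3 and 6 both lie beyond the 14-day limit of the acute studies, so a pooled SR–HS difference in those records is evidence that the effect outlasts the acute window. This stands. A reader might infer that persistence has no test at all, and that would be too strong. What has no test is whether the effect is still present at week 6.

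A reader might also infer that the week-3 and week-6 records were scheduled in order to show persistence. The plan does not say so. Its food intake section gives the interest as diet quality and differences between phases.

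Third, the plan calls the model a repeated-measures one, and the paired tests could be run on week 6. Either is possible, but neither is written, and the independent variables that are listed do not include week. Pooling over visits is the natural reading of an incomplete specification, not something the plan states.

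Finally, the complete fade is a constructed case with assumed SDs, and a significant pooled result in it is correct for Hypothesis 2a. The percentages illustrate the gap and do not predict this trial's result.

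**Conclusion.** The gap between the Aim 2 question and the written intake analysis is real and depends on no numerical assumption: no stated term or contrast separates week 3 from week 6. Its practical size does depend on assumptions. In the full-fade case at SD 500 kcal, a significant pooled result occurs in roughly half to three-quarters of trials if only weeks 3 and 6 are pooled (52–58% at n = 36, 67–73% at n = 50). It occurs in roughly a third to a half if baseline is pooled as well (30–36% and 40–48%). Because that choice changes the figures so much, the role of the baseline record must be settled too.

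The documents do not support the inference that a faded effect will be reported as maintained. They show only that the planned analysis could not reveal the fade.

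**What to change.** - Use the week-3 and week-6 records as the response. Keep the phase-baseline record out of the response and enter it as a covariate.
- Fit sleep, week, sleep-by-week and phase, with the planned covariates and random subject effect.
- Make the week-6 SR–HS contrast, with its confidence interval, the test of maintenance. Report the week-3 contrast and the change between the two, each with a confidence interval. Do not read a non-significant interaction alone as maintenance.
- Keep the pooled SR–HS contrast for Hypothesis 2a, and state which value per phase the paired t-test and Wilcoxon test use.

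No new data are needed. The cost is a few model terms and a less precise estimate than the average, with the power for a maintained effect as shown in the working. The Renewal Information section says the study remains open for analysis and lists reports on lipids, inflammatory markers and cognition, not intake. If intake has already been analysed, the week-6 contrast should be labelled as a later addition.

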**Scientific Abstract:**

Chronic sleep restriction (SR) is highly prevalent in today's modern society and severe sleep deprivation (SD) has been linked to obesity. We are interested in establishing whether sleep could be a causal factor in the etiology of obesity. In a recent meta-analysis, authors concluded that no studies exist to assess the effects of long-term manipulation of sleep duration on obesity risk, and proposed additional research using more standardized methods and measures, as well as evaluations of associated outcomes with sufficient sample sizes to inspect this relationship. We propose a randomized, crossover, outpatient sleep restriction study with 2 phases of 6 wk each. Sixty-six men and pre-menopausal women, age 20-40 y, BMI 20-34.9 kg/m^2 (with parent with BMI >27 kg/m^2 if participant BMI is 20-24.9 kg/m^2), normal sleepers, free of any current and past sleep and psychiatric disorders, diabetes or CVD will be recruited. During the habitual sleep (HS) phase, participants will be asked to follow a fixed bedtime routine based on their screening sleep schedule. During the SR phase, participants will be asked to keep their habitual wake time constant but delay their bedtime to achieve a reduction of 1.5 h in total sleep time. Subjects will have anthropometric measurements taken, will provide a fasting blood sample to examine cardiovascular risk factors, and will then have body composition assessed at baseline and endpoint using magnetic resonance imaging (MRI). Body weight and waist circumference will be measured weekly, fasting blood and urine samples will be taken at baseline, week-3, week-4, and endpoint, during adherence check visits. Doubly labeled water (DLW) will be given at week 4 of each study phase will assess free-living energy expenditure (EE) and the continuous wear of actigraph monitors will provide detailed information on physical activity levels as well as monitor sleep duration. At week 5 of each study phase, a non-fasting blood draw will be taken. The subjects will undergo an fMRI at the end of each phase to assess indices of neuronal activation of brain reward and control centers under food-stimulated conditions. Results of the proposed study will determine whether SR can lead to weight gain, answering the key question of causality. Furthermore, data will be able to generate novel hypotheses related to the role of sleep duration.

and energy balance on cardio-metabolic risk profile and results may provide additional knowledge on which to base public health recommendations for obesity prevention efforts.

